[name]	Yes
[name]	Yes
[name]	No
[name]	No

VII.D.15 *Check all materials that will be used to obtain/document informed consent:*

- Consent Document

VII.D.16 *Are you requesting a [waiver of documentation](#) of consent (either no subject signature or no written document)?*
No

VII.D.19 *Before the subject gives consent to participate are there any screening questions that you need to directly ask the potential subject to determine eligibility for the study?*
No

VII.D.25 *After the subject agrees to participate (signs consent), are there any screening procedures, tests, or studies that need to be done to determine if the subject is eligible to continue participating?*
No

VII.D.27 *Discuss how much time a potential subject will have to agree to consider participation and whether or not they will be able to discuss the study with family/friends before deciding on participation.*
Patients will have as much time as they need to consider participation in this study - there will be no time constraint. They will be free to discuss the study with family/friends before consenting to participate.

VII.D.28 *How long after the subject agrees to participate do study procedures begin?*
Testing will begin within one week of the subject's agreeing to participate in the study.

VII.D.29 *Provide a description of the enrollment and consent process for adult subjects*

- Describe each study population separately including control population
- Include when recruitment and consent materials are used
- Use 3rd person active voice "The Principal Investigator will identify subjects. For example, the principal investigator will identify potential subjects, the study coordinator will discuss the study with subjects over the telephone and schedule the first study visit, etc..."
- Describe the steps that will be taken by the research team to minimize the possibility of coercion or undue influence during the consent process

The Principal Investigator will identify subjects that meet inclusion criteria based on chart review prior to potential subjects' upcoming glaucoma clinic appointments. Potential subjects will be approached at the time of their scheduled appointment to participate in the study. The Principal Investigator and/or research assistant will describe the purpose of the study, study procedure, and risks/benefits of participation prior to obtaining informed consent from the subject. Additionally, the Principal Investigator and/or research assistant will reassure potential subjects that their participation in the study is completely voluntary, they are free to withdraw from the study at any point without consequences, and their decision to participate/not participate will not affect their regular care.

VII.D.37 *Does the study include any form of deception (e.g., providing participants with false information, misleading information, or withholding information about certain study procedures)?*

Examples:

- Procedure includes a cover story that provides a plausible but inaccurate account of the purposes of the research.
- Participants will be provided with false information regarding the particular behaviors of interest in the research.
- Procedures include a confederate pretending to be another participant in the study.
- Participants will be told that the research includes completion of a particular task, when in fact, that task will not be administered.
- Study is designed to introduce a new procedure (or task) that participants are not initially told about.
- If yes, a waiver of informed consent must be requested under question IV.3.

No

VII.E. Project Description (E)

- VII.E.1** *Will subjects be randomized?*
No
- VII.E.3** *Will any questionnaires, surveys, or written assessments be used to obtain data directly from subjects in this study?*
Yes
- VII.E.4** *List all questionnaires, surveys, written assessments and ATTACH each one to the application. (NOTE: You are NOT prohibited from attaching copyrighted materials to this application)*
EyeSimplify Visual Field Satisfaction Survey
- VII.E.5** *Does this project involve creating any audiotapes, videotapes, or photographs?*
No
- VII.E.6** *Provide a detailed description in sequential order of the study procedures following the consent process - DO NOT cut and paste from the Consent Document.*
- Describe study populations separately if they will be participating in different procedures - include CONTROL population if applicable.*
- DESCRIBE:**
- *What subjects will be asked to do/what happens in the study (in sequential order)*
 - *The time period over which procedures will occur*
 - *The time commitment for the subject for individual visits/procedures*
 - *Long-term followup and how it occurs*
- Potential subjects will be approached at the time of their regularly scheduled appointment to participate in this research study. The research assistant will answer any questions potential subjects may have regarding the purpose, procedure, and risks of the study. If they agree to participate, subjects will sign an informed consent.
- In addition to routinely scheduled clinical examination, including visual field testing (VF) with the Humphrey Field Analyzer (HFA), subjects will be asked to complete biweekly VF for six months using EyeSimplify, a novel, web-based VF, at home. Subjects will be instructed to complete the EyeSimplify VF in a quiet, dark room free of distractions. The research assistant will be available via email or telephone to troubleshoot any issues that may arise.
- The EyeSimplify uses a 24-2 examination protocol with a Neighborhood-Zippy Estimation by Sequential Testing (ZEST) testing algorithm. Background brightness will be set to 15.8 ASB. The test will use a scaled white stimulus. Subjects will self-administer the EyeSimplify VF at home. The EyeSimplify VF will be deemed unreliable if FP >15%. The HFA uses a 24-2 examination protocol with a SITA standard testing algorithm. A clinical technician will administer the HFA VF at the University of Iowa Hospitals and Clinics' Glaucoma clinic. The HFA VF will be deemed unreliable if FP >15%. At the conclusion of the study, subjects will complete a satisfaction survey regarding testing using the EyeSimplify VF.
- VII.E.7** *Will you attempt to recontact subjects who are lost to follow-up?*
Yes
- VII.E.8** *Describe - any procedures need to be included in the consent:*
If a subject fails to complete a scheduled home visual field test, the PI or research assistant will reach out to the patient via email and/or telephone to determine the cause of the missed test. If the patient can be contacted and wishes to continue participating in the study, the PI or research assistant will prompt the subject to complete the exam. If a patient misses a second scheduled test, the patient will be considered lost to follow-up and will not be contacted again.
- VII.E.9** *Will subjects be provided any compensation for participating in this study?*
No

VIII. Risks

- VIII.1** *What are the risks to subjects including*
- *emotional or psychological*
- *financial*
- *legal or social*
- *physical?*
Loss of time and confidentiality
- VIII.2** *What have you done to minimize the risks?*
- *If applicable to this study ALSO include:*
 - *How you (members of your research team at Iowa) will monitor the safety of individual subjects.*
 - *Include a description of the availability of medical or psychological resources that subjects might require as a consequence of participating in this research and how referral will occur if necessary (e.g. availability of emergency medical care, psychological counseling, etc.)*

Patient privacy will be protected by separating patient identifiers from the data and storing the data on a password-protected computer in a locked office within the Ophthalmology Department. To prevent a loss of confidentiality from occurring, all data will be located on a UIHC encrypted, password-protected Department of Ophthalmology server. Only designated research team members and PI will have access to the drive. Any paper documents will be kept in a locked file cabinet in the principal investigator's office.

All data collected by M&S Technologies will be stored in a secure, encrypted, HIPAA-compliant database. De-identified subject data is ultimately aggregated for quality improvement purposes by M&S Technologies.

The study utilizes data generated as a consequence of routine clinical practice, as well as additional home, web-based visual field tests. The study poses no therapeutic questions and no interventions; no treatment is directed by the study. Therefore, the study poses no substantive risk to the patient other than loss of time and confidentiality. It does not impose any significant burden on the patient.

VIII.3 Does this study have a plan to have an individual or committee reviewed combined data from all subjects on a periodic basis (such as summary or aggregate safety and/or efficacy data)?
No

IX. Benefits

IX.1 What are the direct benefits to the subject (do not include compensation or hypothesized results)?

None

IX.2 What are the potential benefits to society in terms of knowledge to be gained as a result of this project?

To date, there is no universally accepted method for monitoring glaucoma at home. Society may benefit from this study by validation of a novel home, web-based visual field test that may decrease cost and discomfort of visual field testing and increase its accessibility.

X. Privacy & Confidentiality

X.1 What are you doing to protect the [privacy](#) interests of the subjects?

All data collected into the research database will only be accessed by the principal investigator (PI) and/or designated key research team members. Patient identifiers and/or data (i.e., name, medical record number) will be collected but will be replaced by study numbers in the analytical file. Subjects' data will be de-identified immediately after completion of the data collection per HIPAA regulations. Subject identifiers will not be viewed by non-study members and will not be published. Subject number identifiers will be used rather than patient names. No other identifiable information will be recorded. All efforts will be made to protect subject's rights to privacy by collecting only the minimum information necessary to meet the aims of this study. Information collected is similar to that which the clinician would encounter for the subject's clinical care.

Subject demographic and testing data will be collected and stored by M&S Technologies in a secure, encrypted, HIPAA-compliant database. Subject identifiers are encrypted upon storage. Subject data is only shared with M&S-affiliated consultants and service providers, healthcare providers using EyeSimplify, and for law enforcement or judicial proceedings as permitted by law. De-identified subject data is ultimately aggregated for quality improvement by M&S Technologies.

X.2 Are you collecting the Social Security Number of any subjects for any purpose?

No

X.4 How will information/data be collected and stored for this study (check all that apply):

- Electronic records (computer files, electronic databases, etc.) - All electronic files will be kept as files on an encrypted, password-protected UIHC Department of Ophthalmology network server. There will be no identifiers or link available on any transferred data; therefore, there will be no way to compromise patients' privacy or confidentiality.
 - Name - [name]
 - Title - Senior IT Support Consultant
 - University Job Classification - Faculty/Staff
- Paper/hard copy records (hard copy surveys, questionnaires, case report forms, pictures, etc.) - Informed consent documents will be transported directly from the UIHC Glaucoma clinic to a locked file cabinet in the PI's office within the Department of Ophthalmology and Visual Sciences immediately following the study recruitment clinical encounter by the PI or research assistant. These documents will remain in this locked cabinet for the duration of the study.

X.5 Do the confidentiality protections indicated above allow only members of the research team to access the data/specimens?

No

X.6 Describe

M&S Technologies, the developers of the EyeSimplify web-based visual field test, maintain a secure, encrypted, HIPAA-compliant database of patient testing information. This database includes study ID (de-identified), birth year, and experimental visual field testing data. M&S Technologies does not have access to any additional patient information.

X.7 Does your study meet the NIH criteria for a [Certificate of Confidentiality](#) or will you be applying for Certificate of Confidentiality?

No

XI. Data Analysis

XI.1 Describe the analysis methods you will use, including, if applicable, the variables you will analyze

Variables: Clinical data including age, gender, ethnicity, Humphry Visual Field performance, EyeSimplify Visual Field performance, and satisfaction survey will be collected and analyzed.

Data analysis: Humphrey Visual Field Guided Progression Analysis (GPA) and EyeSimplify Visual Field mean deviation linear trending will be compared using Bland-Altman analysis.

XI.2 Provide the rationale or power analysis to support the number of subjects proposed to complete this study.

A similar study investigating home visual field testing using the Melbourne Rapid Fields iPad application (Glance Optical Pty., Ltd., Melbourne, Australia) recruited 47 subject, of which 43% (n = 20) were analyzed (Prea SM, Vingrys AJ, Kong GYX. Test Reliability and Compliance to a Twelve-Month Visual Field Telemedicine Study in Glaucoma Patients. J Clin Med. Jul 25 2022;11(15)doi:10.3390/jcm11154317).

XII. Future Research

XII.1 Do you wish to keep any information about subjects involved with this research project so that members of the current research team may contact them in the future for your own research projects?

No

XII.2 *Do you wish to keep any information about subjects involved with this research project so that [other researchers](#) may contact them for future research?*
No

XII.4 *Does this project involve storing any data, tissues or specimens for future research?*
Yes – contribution(s) for future use is mandatory for participation in the study

**Human Subjects Office/
Institutional Review Board (IRB)**

[name]
[name]
[name]
[contact] [contact]
[contact]
<http://research.uiowa.edu/hso>

IRB ID #: 202207403

To: [name]

From: IRB-01 DHHS Registration # IRB000000099,
Univ of Iowa, DHHS Federalwide Assurance # FWA00003007

Re: Visual Field Telemedicine in Glaucoma Patients using a Web Browser-Based Test Strategy

Protocol Number:

Closure Date: 09/05/25

Source of Support: American Glaucoma Society

Investigational New Drug/Biologic Name:
Investigational New Drug/Biologic Number:
Name of Sponsor who holds IND:

Investigational Device Name:
Investigational Device Number:
Sponsor who holds IDE:

The following documents have been submitted with the closure notification:
No new attachments.

This closure is acknowledged and has been electronically filed. IRB approval is no longer valid for the above-named project.

Study Closure: Closing a study with the IRB is a permanent action and cannot be undone. The PI is required to notify all research team members and participating research sites (as applicable) of the closure. Closing a project means:

- The research is permanently closed to accrual/enrollment
- All subjects have completed all research related activities
- Collection and use of private identifiable information is complete
- Analysis of private identifiable information is complete

The following applies to this research even after study closure:

Audits: Your research records may be audited at any time during or after the implementation of your project. Audits may also occur after the study has been formally closed with the IRB.

ClinicalTrials.gov reporting: If Clinicaltrials.gov results reporting is required based on FDA regulations (e.g.,

Applicable Clinical Trial) or federal funding (e.g., NIH clinical trials), then the results must have been submitted on the ClinicalTrials.gov website prior to the study's closure.

University of Iowa Research Data: In accordance with the University of Iowa's copyright policy ([Operations Manual Section V\(30.4\)](#)), research data generated as part of a University of Iowa research study is owned by the University. All research data policies remain in effect even after the research has ended. For additional information regarding the research data policy and any requirements for data leaving the University of Iowa, visit the [Division of Sponsored Programs](#) website under [Data Use Agreements](#).

Record-Keeping/Retention Requirements: Federal and University policies require that all research records be maintained for a period of three (3) years following the close of the research project. For research that involves drugs or devices seeking FDA approval, the research records must be kept for a period of three years after the FDA has taken final action on the marketing application. For research that involves Protected Health Information (PHI) under HIPAA, the research records must be kept for a period of six (6) years following the close of the research project.

Special Note: The above-named project details can be accessed via HawkIRB by updating the project status filter from "open" to "any."

Additional Information: Complete information regarding research involving human subjects at The University of Iowa is available in the "Investigator's Guide to Human Subjects Research." Research investigators are expected to comply with these policies and procedures, and to be familiar with the University's Federalwide Assurance, the Belmont Report, 45CFR46, 21CFR50/52, and other applicable regulations prior to conducting the research. These documents and IRB application and related forms are available on the Human Subjects Office website or are available by calling [contact].

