Following study recruitment, subjects will be asked to take EyeSimplify visual field tests at home biweekly for six months. They will have no additional responsibilities between tests. Subjects will access the EyeSimplify web browser on their personal electronic devices using a link and login credentials provided to them by a research assistant. Upon logging into the EyeSimplify web browser, subjects will click the "Start Test" button found along the left side of the window and follow the prompts presented on screen to calibrate their screen. Screen calibration involves holding a driver's license/credit card/ID to the screen to ensure the test window is the appropriate dimensions. Following screen calibration, subjects will follow the test prompts presented on screen to complete their visual field test. Test results are automatically sent to the research assistant who issued the exam, so subjects may exit the browser after each test. Upon study completion, subjects will be asked to fill out a brief satisfaction survey.

M&S Technologies is the developer of the EyeSimplify web-based visual field test. [name], [name], and [name] have no financial or intellectual relationship with M&S Technologies, aside from the current study and an additional study under IRB review investigating the Pico Virtual Reality Headset visual field test.

As the developers of the web-based visual field test, M&S Technologies maintains a secure, encrypted, HIPAA-compliant database of EyeSimplify users. This database includes patient profiles containing unique patient IDs (de-identified), birth year, and visual field testing results. Outside of this testing information, M&S Technologies does not have access to any additional patient information.

I.5

Specify your research question(s), study aims or hypotheses (do not indicate "see protocol")
Aim 1: Determine test reliability of the EyeSimplify (M&S Technologies, Niles, IL) home, web-based visual field test in glaucoma patients.
Aim 2: Determine the concordance of EyeSimplify to the Humphrey Visual Field Analyzer (Carl Zeiss Meditec Inc., Dublin, CA) in identifying visual field loss progression.
Aim 3: Determine patient compliance with and tolerance of biweekly EyeSimplify testing for a 6 month period, assessed by test recordkeeping and a patient experience survey.

Primary Hypothesis: The EyeSimplify visual field test will produce reliable visual field testing data.

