Secondary Hypothesis: The EyeSimplify visual field test will be non-inferior to the Humphrey Visual Field Analyzer in identifying glaucomatous progression trends.

I.6

Background and significance and/or Preliminary studies related to this project. (do not indicate "see protocol")
Glaucoma is the leading cause of irreversible blindness worldwide (1-2). Standard Automated Perimetry is the current accepted standard for diagnosis and monitoring of glaucomatous visual field loss (3), and the Humphrey Visual Field Analyzer (HFA; Carl Zeiss Meditec Inc., Dublin, CA) is the automated perimeter that is most frequently used due to it currently having the largest market share. The HFA is a useful clinical tool; however, it is a large, expensive device. Testing takes approximately seven minutes per eye when using the Swedish Interactive Threshold Algorithm (SITA) Standard testing algorithm, and testing is typically only done at 6-12 month intervals. Recently, there has been interest in the development of alternative methods to monitor visual field progression outside of the clinic setting (4). EyeSimplify (M&S Technologies, Niles, IL) is a web-based visual field test that aims to increase the frequency at which patients can test their visual fields, improve accessibility to visual field testing, and potentially identify visual field loss progression more quickly.

I.7

Literature cited / references (if attaching a grant or protocol enter N/A).
1. Quigley HA. Number of people with glaucoma worldwide. Br J Ophthalmol. May 1996;80(5):389-93. doi:10.1136/bjo.80.5.389

doi:10.1136/bjo.2005.081224

II. Research Team

II.1

Principal Investigator

Name	E-mail	College
[name]	[contact]	Carver College of Medicine

II.2

Team Members

UI Team Members

Name	E-mail	College	Contact	Key Prsn	UI COI	VAMC COI	Consent Process Involvement	Deactivated
[name]	[contact]	Carver College of Medicine	Yes	Yes	No		Yes	No

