V.27 *Will the study involve the use of the I-CTMS (OnCore) for clinical trial data management? Select yes if any or all of the following apply:*

- *Any study required to register subjects in EPIC are encouraged to use the I-CTMS*
- *Best practice is to use the I-CTMS for any new study that involves subject tracking or sponsor invoicing*

Note: This question is for non-oncology studies only. For oncology studies use existing HCCC OnCore processes by selecting V.22
No

VI. Subjects

VI.1 *How many adult subjects do you expect to consent or enroll for this project?*
50

VI.2 *What is the age of the youngest adult subject?*
18.0

VI.3 *What is the age of the oldest adult subject?*
100.0

VI.4 *What is the percentage of adult male subjects?*
50

VI.5 *What is the percentage of adult female subjects?*
50

VI.6 *How many minor subjects do you expect to consent or enroll for this project?*
0

VI.13 *Describe EACH of your subject populations*

- *Include description of any control group(s)*
- *Specify the Inclusion/Exclusion criteria for EACH group*

Inclusion criteria: Patients older than 18 years of age with suspected, mild, moderate, or severe glaucoma

Exclusion criteria: Non-English speakers, patients with systemic or ocular disease affecting central vision, neurocognitive or psychiatric patients that are unable to perform testing, astigmatism >+2.00/-2.00 diopters

VI.14 *Provide an estimate of the total number of subjects that would be eligible for inclusion in each of your study populations (include your control population if applicable)*
450

VI.15 *Describe how you will have access to each of your study populations in sufficient number to meet your recruitment goals.*
Patients at the University of Iowa Hospitals and Clinics' Glaucoma clinic will be approached at the time of their scheduled appointments to determine if they are interested in participating in this research study.

VI.16 *Do you plan to recruit/enroll non-English speaking people?*
No

VI.18 *Do you propose to enroll any of the following in this study as subjects?*

- *Employee of the PI or employee of a research team member*
- *Individual supervised by PI or supervised by member of research team*
- *Individual subordinate to the PI or subordinate to any member of the research team*
- *Student or trainee under the direction of the PI or under the direction of a member of the research team*

No

VI.20 *Will subjects provide any information about their relatives?*
No

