Medical record number	
Health plan beneficiary or account numbers	
Certificate/license numbers	
Vehicle identifiers and serial numbers or license numbers	
Device identifiers or serial numbers	
Web URLs	
Internet Protocol (IP) address numbers	
Biometric identifiers including finger/voice prints	
Full face photographic images or any comparable images	
None of the above	

- VII.D.2.a** *List ALL of the variables, including any identifiers not previously entered or links to identifiers you plan to obtain/use for purposes of this study. (The information accessed should be the minimum data variables necessary for performing the desired analysis.)*

Data elements to be collected will include name, MRN, age, and glaucoma diagnosis/severity.

- VII.D.3** *Describe why you could not practicably recruit subjects without access to and use of the information described above*

Without the above, there would be many patients who would not meet inclusion or exclusion criteria after initial assessment. Using the above data will allow for a better patient experience while enrolling in this study, as well as better specificity in identifying the population we intend to recruit.

- VII.D.4** *Describe why you could not practicably obtain authorization from potential subjects to review their patient or clinic records for recruitment purposes.*

This study intends to review patients from a physician's practice panel to identify recruits. To request written authorization from all patients prior to identification for study inclusion or exclusion would require contacting all of the physician's patients prior to identification, for authorization to review records that the physician is already reviewing for their clinical care. This would require an inordinate amount of time, administrative labor and solicitation of thousands of patients.

- VII.D.5** *Describe plans to protect the identifiers from improper use or disclosure*

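### Aim 2 requires no Humphrey field series and pools stable with progressing eyes, so its single agreement result cannot show that EyeSimplify identifies progression

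*Combined protocol and SAP*

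**What the plan says.** Aim 2 (I.5) is the concordance of EyeSimplify with the HFA "in identifying visual field loss progression". The secondary hypothesis, which follows it, claims non-inferiority to the HFA for identifying progression trends.

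Entry (VI.13) reads: "Inclusion criteria: Patients older than 18 years of age with suspected, mild, moderate, or severe glaucoma". The exclusions begin "Exclusion criteria: Non-English speakers, patients with systemic or ocular disease affecting central vision, neurocognitive or psychiatric patients that are unable to perform testing" and add an astigmatism limit; none concerns HFA history. The variables listed for finding recruits (VII.D.2.a) are limited: "Data elements to be collected will include name, MRN, age, and glaucoma diagnosis/severity". Screening is by chart review before the visit (VII.D.29), and VII.D.25 plans no eligibility tests after consent.

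The only analysis stated for Aim 2 (XI.1) is that "Humphrey Visual Field Guided Progression Analysis (GPA) and EyeSimplify Visual Field mean deviation linear trending will be compared" by Bland-Altman analysis. It mentions no analysis set, no split by progression status and no rule for an eye without an HFA trend.

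HFA fields are taken at routine visits (VII.E.6), and the background (I.6) says that "testing is typically only done at 6-12 month intervals". Home testing is biweekly for six months. The summary (I.4) does plan retrospective record review, with HFA performance among the data collected.

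**The concern.** Two things that Aim 2 depends on are left to chance. The first is the HFA reference trend. The study itself adds too few HFA fields to form one, so it must come from earlier fields that entry does not require.

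The second is the presence of eyes that are progressing. Where both true trends are flat, the comparison measures noise and cannot reveal whether the home test would have picked up a decline. With every eye in one pooled analysis, a small mean difference could be reported as support for identifying progression when that ability was hardly examined.

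**Working it through.** The plan has no power calculation for Aim 2 to reproduce. XI.2 cites only a precedent with 47 recruited and 20 analysed: 20/47 = 42.6%, matching the stated 43%.

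**Inputs from the documents.** N = 50 (VI.1); six months of biweekly home tests (VII.E.6); HFA every 6-12 months (I.6); precedent 20/47 (XI.2).

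**Assumptions, not in the documents.** One eye per subject; progressor share 5%, 10% or 20%; test-retest SD of MD 1 dB on both devices; the GPA side read as an MD slope in dB/yr; true slope zero in stable eyes and -1 to -2 dB/yr in progressing eyes; share without a usable HFA series 2%, 6% or 10%.

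**1. HFA fields from the study itself.** A subject has one field at enrolment and, at a 6-month interval, one more at the end; at 12 months, none. One field gives no slope. Two fields at 0 and 0.5 years give Sxx = 2 x 0.25² = 0.125, so the slope SE is 1/√0.125 = 2.83 dB/yr, with no residual degrees of freedom. A usable trend needs earlier fields.

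**2. Subjects without a series.** Expected number = 50s; chance of at least one = 1 - (1-s)^50.

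| Assumed share s | Expected of 50 | Chance of at least one |
|---|---|---|
| 2% | 1 | 64% |
| 6% | 3 | 95.5% |
| 10% | 5 | 99.5% |

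**3. Noise in the planned comparison.** For 13 tests at two-week spacing, Sxx = 4 x 182 = 728 weeks² = 0.269 years², and the EyeSimplify slope SE is 1/√0.269 = 1.93 dB/yr. For five HFA fields over two years (an illustrative series), Sxx = 2.5 and the SE is 0.63. The SD of the difference is √(1.93² + 0.63²) = 2.03, so the limits of agreement are about ±1.96 x 2.03 = ±4.0 dB/yr. If biweekly means twice a week (52 tests, SE 0.96), they are about ±2.25.

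**4. What stable eyes can show.** Let θ be the true HFA slope and suppose that EyeSimplify captures a fraction b of it. The expected difference, EyeSimplify minus HFA, is (b-1)θ. With θ = 0 this is zero for every b, so stable eyes carry no information on b. Pooled over all eyes, the mean shift is p(b-1)θ, where p is the progressor share. For a test blind to progression (b = 0):

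- p = 10%, θ = -1: shift 0.10 dB/yr
- p = 20%, θ = -2: shift 0.40 dB/yr

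The 95% half-width for the pooled mean difference with 50 eyes is 1.96 x 2.03/√50 = 0.56 dB/yr. Both shifts lie inside it. With 52 home tests the half-width is 1.96 x 1.15/√50 = 0.32, so the larger shift would show and the smaller would not.

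**5. Eyes that inform detection.** If every progressor were detected, the lower exact 95% limit for n of n is 0.025^(1/n).

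| Assumed p | Progressors of 50 | Lower limit if all detected | Progressors of 21 |
|---|---|---|---|
| 5% | 2.5 | 16% (2/2) | 1.1 |
| 10% | 5 | 48% (5/5) | 2.1 |
| 20% | 10 | 69% (10/10) | 4.2 |

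The last column applies the precedent's analysed share: 50 x 20/47 = 21.3.

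**The case against.** The strongest reply is that the retrospective review in I.4 will supply earlier HFA fields for many patients of a glaucoma clinic, and that analysts would drop eyes without a GPA trend anyway. That largely stands. A reader might infer that some subjects are bound to lack an HFA trend. The documents do not support this: they give no such share, and step 2 rests on assumed ones. What remains is that the review collects whatever exists and that no rule is written down.

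A reader might also infer that pooling stable eyes will produce flattering agreement. That would suit a count of matching progressing/stable calls, which the plan does not use. Under Bland-Altman analysis, noisy six-month slopes could give wide limits, as step 3 shows. The result may therefore look poor rather than good. In neither case does it test detection.

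A third objection is that case mix is not the only limit. With an SE of 1.93 dB/yr, a true slope of -1 to -2 dB/yr would be distinguished from zero with only about 13-27% power (one-sided 5%), or 27-67% with 52 tests. GPA status also describes past progression, which need not continue during the home-test months. Both points stand, and they limit what the fix can achieve.

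Finally, one might conclude that progressing patients should be recruited first. The documents do not call for it. Reliability is the primary hypothesis and compliance is Aim 3, and broad entry suits both. Preferential approach would change that sample and worsen regression to the mean.

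**Conclusion.** The concern holds in a limited form. Nothing in the entry criteria, recruitment variables or analysis section secures an HFA series or identifies progressing eyes, and XI.1 pools all eyes. A pooled agreement result can describe slope agreement. It cannot support concordance or non-inferiority in identifying progression.

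The size depends on figures the plan does not give. At assumed progressor shares of 5-20%, about 2.5 to 10 of 50 subjects bear on detection, and about 1 to 4 if only some 21 are analysable. That stable eyes carry no information on detection follows from step 4 and does not depend on the assumed shares or SDs. Aims 1 and 3 are unaffected. This is a worthwhile, inexpensive improvement to a secondary aim, not a flaw in the study as a whole.

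**What to change.** In XI.1:

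1. Limit the Aim 2 set to eyes with a reliable HFA series (false positives at most 15%, the plan's own rule in VII.E.6) long enough for a GPA trend. State the minimum number of fields, which the documents do not give, and report how many subjects lack such a series. All subjects stay in Aims 1 and 3.
2. Classify each eye from existing HFA records as GPA-progressing, GPA-stable or suspect. Add HFA history to the record variables in VII.D.2.a.
3. Report the HFA/EyeSimplify comparison separately by that status, with the number of progressing eyes and confidence intervals.
4. Base any statement about identifying progression on the progressing eyes only. If they are too few, limit Aim 2 to slope agreement.

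The cost is a few sentences and one more item at a chart review that already takes place; no extra subjects, visits or tests are needed. The downsides should be stated in the report. The progressing stratum will be small and imprecise, and GPA status reflects past change. Grouping eyes by their HFA result also invites regression to the mean: observed HFA slopes in the progressing group will tend to be steeper than the true ones, which makes EyeSimplify look too flat there.

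The closure notice (09/05/25) ends the use of identifiable data. From that point, only the analysis-set and reporting steps can be applied, and only as far as the retained HFA data allow.
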